	
 • Phase III: T-test between Arm A vs Arm B at FU3. • Clinical Response Prediction will be addressed by multiple regression examining relationships between baseline predictor variables (i.e; cognitive profile) and cognitive change scores. • Sample Size and Power This study is powered on the basis of a relative effect size (RES) on Global Cognition of 0.44 at the end of the Phase I RCT (based on average from our Timecourse Trial⁵ and NHMRC SMART trial⁶). Designate power of 0.80 controlling α at 0.05 translates to a required sample size of N=52 (calculated using G*Power 3.1 based on ANOVA repeated measures within-between interaction test, 2 groups, 2 time-points, within subject autocorrelation =0.4, equivalent effect size of [v]=0.22). A sample of N=62 (rounded up from 61) will be recruited to allow for 15% overall attrition (as per Timecourse Trial extrapolated to 9-months).
Duration of the study	3 years

GLOSSARY OF ABBREVIATIONS

ABBREVIATION	TERM
CCT	Computerised Cognitive Training
MCI	Mild Cognitive Impairment
BTS	NHMRC Maintain Your Brain Trial Brain Training System
ADCS-ADL	Alzheimer’s Disease Cooperative Study-Activities of Daily Living
WHOQOL	World Health Organisation Quality of Life
GDS	Geriatric Depression Scale
PSQI	Pittsburgh Sleep Quality Index
APOE 4	Apolipoprotein E 4
BDNF	Brain-derived neurotrophic factor

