The endpoint of FU3 will assess the long-term implication of immediate compared to delayed intervention. If over a 9-month period the timing of a 3-month CCT intervention does not matter, i.e., both arms are cognitively equivalent at the end, then that may influence and inform the distribution of CCT resources in clinics and the community.

Figure 3: Study Hypotheses

Hypotheses

es = effect size

e = endpoint

Primary

Phase I: $es_{A1} > es_{B1}$

Secondary

Phase II: $es_{A1} > es_{B2}$

Phase III: $e_{A3} = e_{B3}$

Assess for eligibility:
Multi-domain MCI criteria
Sleep disturbance criteria
No major neurological/psychiatric/mood disorder

Exclude:
Not meet inclusion criteria
Declined to participate

Written Consent

Enrolment

Baseline Measurements:

- Neuropsychological tests
- Sleep-wake quality
- DNA saliva swab
- Economic decision making

Randomised (n=62)

ARM A
(n=32)

Allocation

ARM B
(n=32)

- Neuropsychological outcomes
- Sleep-wake quality
- Neuroimaging
- Economic decision making
- Review for any adverse events
- Lost to follow-up (reasons)

Follow-up 1
3-months after baseline

- Neuropsychological outcomes
- Sleep-wake quality
- Neuroimaging
- Economic decision making
- Review for any adverse events
- Lost to follow-up (reasons)

- Neuropsychological outcomes
- Sleep-wake quality
- Review for any adverse events
- Lost to follow-up (reasons)

Follow-up 2
6-months after baseline

- Neuropsychological outcomes
- Sleep-wake quality
- Review for any adverse events
- Lost to follow-up (reasons)

- Neuropsychological outcomes
- Sleep-wake quality
- Review for any adverse events
- Lost to follow-up (reasons)

Follow-up 3
9-months after baseline

- Neuropsychological outcomes
- Sleep-wake quality
- Review for any adverse events
- Lost to follow-up (reasons)

- Intention-to-treat analyses: Linear Mixed Model
- Clinical response prediction: Multiple regression
- Excluded from analysis (reasons)

Analysis

- Intention-to-treat analyses: Linear Mixed Model
- Clinical response prediction: Multiple regression
- Excluded from analysis (reasons)

Screening

MCI criteria

MCI is diagnosed according to the Winblad et al 2004 criteria²² confirmed on the basis of consensus rating of multiple clinicians within the memory center.

Typically, this includes a geriatrician or neurologist and two clinical neuropsychologists who review the individual's clinical profile and neuropsychological results.

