10. STATISTICAL METHODS

10.1 Sample Size Estimation

This study is powered on the basis of a relative effect size (RES) on Global Cognition of 0.44 at the end of the Phase I RCT (based on average from our Timecourse Trial⁵ and NHMRC SMART trial⁶). Designate power of 0.80 controlling α at 0.05 translates to a required sample size of N=52 (calculated using G*Power 3.1 based on ANOVA repeated measures within-between interaction test, 2 groups, 2 time-points, within subject autocorrelation =0.4, equivalent effect size of $[\eta^2]=0.22$). A sample of N=62 (rounded up from 61) will be recruited to allow for 15% overall attrition (as per Timecourse Trial extrapolated to 9-months).

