10.3 Statistical Analysis Plan

Phase I: An *intention-to-treat* approach using recommended Linear Mixed Modelling⁴ will evaluate a model including main effects for Group (Arm A vs Arm B), Time (BL vs FU1) and the main interaction term of interest: Group X Time. Covariates will only be added if baseline differences are noted between groups.

Phase II Linear Mixed Modelling⁴ will evaluate a model including main effects for Group (Arm A vs Arm B), Time (Arm A BL vs FU1, Arm B **FU1 vs FU2**) and the main interaction term of interest: Group X Time. An additional covariate of initial global cognitive status will be added to this analysis to control for different potential starting points for the two arms at the different timepoints.

Phase III: Equivalence of the two arms at follow up III will be tested using a two one-sided test (TOST⁴²).

Clinical Response Prediction will be addressed by multiple regression examining relationships between baseline predictor variables (i.e; cognitive profile) and cognitive change scores.

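### FU3 equivalence is read as showing that the timing of CCT does not matter, with no condition on Phase I, so an inert CCT could support the same message as an effective one

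*Protocol*

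**What the plan says.** Section 4.2 (Study Design) describes the FU3 endpoint as the long-term comparison of immediate with delayed training. It considers the case in which "the timing of a 3-month CCT intervention does not matter, i.e., both arms are cognitively equivalent at the end", and continues: "then that may influence and inform the distribution of CCT resources in clinics and the community". Figure 3 in the same section lists equality of the two arms at FU3 as the Phase III hypothesis. It labels Phase I primary and Phases II and III secondary, and states no dependence between them.

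Section 10.3 fixes the test: "Equivalence of the two arms at follow up III will be tested using a two one-sided test". The synopsis names a different one: "T-test between Arm A vs Arm B at FU3". Neither place makes the reading conditional on Phase I or on a gain in either arm. No equivalence margin is given.

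Section 5.1 says that both arms receive the same 24-session course and differ only in when it is given. Section 2.3 promises, without a condition, that the trial will clarify whether timing of onset matters.

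**The concern.** The Phase III reading has one input: the difference between arms in global cognition at FU3. By then both arms have had the same training and there is no untreated comparator. If CCT does nothing, the expected difference is zero. If CCT works and a three-month delay is harmless, the expected difference is also zero. An equivalence test passes most often at zero, so it treats the two situations alike. In the usual term, the comparison lacks assay sensitivity: a statement that timing does not matter has content only if there is an effect for timing to change.

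At stake is the practical message. FU3 equivalence could be used to support giving CCT now or three months later when the trial has not shown that CCT helps at either time. The extra comparisons in the synopsis (Arm A after Phase I with Arm B after Phase II, and Arm A after Phase II with Arm B after Phase III) do not resolve this. They too come out equal if CCT is inert and scores are otherwise stable.

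**Working it through.** **Inputs.** From section 10.1: α 0.05, power 0.80, 52 evaluable participants, correlation 0.4, 15% attrition, 62 recruited. The synopsis gives the "equivalent effect size of [v]=0.22". Allocation is 1:1, so 26 per arm. Assumed: SD 1 as the unit, one-sided 5% for each TOST test, equal correlation between all visits, and margins from 0.44 to 0.8 SD because none is stated.

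**Step 1: the plan's own figure.** The plan states: "Designate power of 0.80 controlling α at 0.05 translates to a required sample size of N=52". Taking 0.22 as f in the repeated-measures interaction test, λ = f² × N × m / (1 − ρ) = 0.0484 × 52 × 2 / 0.6 = 8.39. On F(1, 50) this gives power 0.811; at N = 50 it is 0.795. So 52 is the smallest even N, and 52 / 0.85 = 61.2, rounded up to 62. The figure reproduces.

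**Step 2: the FU3 test when the true difference is zero.** TOST passes if |d| + t × s × √(2/26) is below the margin, where t(0.95; 50 df) = 1.676 and √(2/26) = 0.277. At s = 1 the added term is 1.676 × 0.277 = 0.465, so a margin of 0.44 SD can pass only when the observed SD is low. The pass rates are in the second column of the table below; the rate reaches about 50% near 0.65 SD. If all 62 were analysed (31 per arm), the rates at 0.44, 0.5 and 0.8 SD would be about 8%, 24% and 86%.

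At 0.8 SD the pass rate for true FU3 differences of 0, 0.22 and 0.44 SD is about 77%, 64% and 35%. It is highest at zero, which is where an inert CCT lies and also where an effective CCT with irrelevant timing lies.

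If the synopsis t-test were used and non-significance read as equality, a zero difference would be called equal 95% of the time.

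**Step 3: chance that Phase I favours CCT.** The change from baseline to FU1 has SD √(2 × (1 − 0.4)) = 1.095, so the standard error of the difference in change is 1.095 × 0.277 = 0.304.
- Inert CCT: 0.025 (significant in the favourable direction only).
- Planned power: √8.39 = 2.90, and 2.90 × 0.304 = 0.88 SD difference in change; probability 0.811.
- True difference in change of 0.44 SD (the RES of 0.44 read in baseline SD units, an assumption): probability about 0.295.

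**Step 4: both conditions together.** With equal correlations, the Phase I change contrast and the FU3 difference have covariance proportional to 0.4 − 0.4 = 0, so the probabilities multiply. Simulation of baseline, FU1 and FU3 agreed with these products.

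| Margin (SD) | FU3 passes, no condition | With condition, inert CCT (× 0.025) | With condition, planned power (× 0.811) | With condition, 0.44 SD effect (× 0.295) |
|---|---|---|---|---|
| 0.44 | 3% | under 0.1% | 2% | 1% |
| 0.5 | 12% | 0.3% | 10% | 4% |
| 0.7 | 60% | 1.5% | 49% | 18% |
| 0.8 | 77% | 1.9% | 62% | 23% |

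The second column holds for an inert CCT and for an effective CCT with no FU3 difference. Under an inert CCT, 1 − 0.025 = 97.5% of FU3 passes would accompany a Phase I that did not favour CCT.

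**The case against.** The sentence in section 4.2 is rationale and is hedged: it begins with a condition and says only that the result may inform resource distribution. Phase I is the primary outcome and would be reported beside FU3, so the trial as a whole can distinguish an effective CCT from an inert one. Section 6.9 makes post-trial advice depend on the trial's results generally. Rules on testing order are often left to a statistical analysis plan, which is not at hand. A condition on Phase I also has a real price: at a true effect of 0.44 SD it would suppress most correct equivalence conclusions.

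Much of this stands, and it rules out three stronger readings that a reader might infer.
- That a null trial would most likely deliver a positive timing message. Under TOST this needs a margin above about 0.65 SD, and none is stated. The 95% figure needs a non-significant t-test to be read as equality, which the synopsis does not say.
- That the rule favours an inert CCT over all other states. It is a tie: an effective CCT with irrelevant timing, or one whose benefit has fully washed out by FU3, gives the same pass rate.
- That Phase II needs the same condition. Phase II is hypothesised as a larger effect in Arm A than in Arm B, and an inert CCT does not make that easier to show.

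What does not stand is that this is only a detail deferred to another document. The protocol itself equates FU3 equivalence with timing being irrelevant and itself fixes the test.

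**Conclusion.** The point holds as a cheap improvement. The protocol states an inference that FU3 equivalence cannot support alone, because an inert CCT and an effective CCT with irrelevant timing produce the same FU3 result. It could therefore yield an unsupported message about timing; the documents do not show that it would.

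The size depends on the missing margin. For an inert CCT with 26 per arm, the chance runs from about 3% at 0.44 SD to 77% at 0.8 SD. These figures assume SD 1, one-sided 5% tests and complete FU3 data on 52 participants. The figures with the Phase I condition also assume a correlation of 0.4 between all visits. The logical gap depends on none of these.

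**What to change.** For Phase III only, add to sections 4.2 and 10.3:

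> The conclusion that timing of CCT does not matter will be drawn from FU3 equivalence only if the Phase I Group x Time effect favours CCT at the stated alpha. Otherwise the FU3 difference is reported with its confidence interval beside the Phase I estimate, and no conclusion on timing or distribution of CCT is drawn.

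This costs two sentences and needs no new data or participants. The downside is that the timing result becomes descriptive whenever Phase I is not significant, and that loss should be accepted openly. It is moderate if the effect is as large as the sample size calculation implies, and severe if the true difference in change is 0.44 SD (last two columns of the table).

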4.2 Study Design

This clinical trial adheres to the conceptual and ethical framework for prevention trials articulated by Peters et al, in which long-term intervention in individuals at-risk for dementia should be correspondingly low-risk²¹. Our experience across four major longitudinal RCTs of CCT has been of no adverse events.

MCI clients that meet basic entry criteria will be recruited from the Healthy Brain Ageing (HBA) clinic, Brain and Mind Centre, University of Sydney (head: [name]) and the Memory Clinic of the Prince of Wales Hospital (head: [name]). Any additional assessments required beyond clinic-based tests, and all intervention procedures, will take place at the Brain and Mind Centre, Sydney, Australia.

The study will consist of three phases and follow-up assessments designed to produce distinct outcomes (refer to **Figure 3**).

Subjects will be randomly allocated in a 1:1 ratio to either ARM A: immediate intervention or ARM B: delayed intervention. Those in ARM A will commence supervised, centre-based multi-domain CCT twice a week, 1 hour per session for 3 months. The main endpoint at the end of Phase I will be to determine whether CCT can improve cognitive function in comparison to a waitlist control. For ARM A, we hypothesize that CCT will lead to an improvement in global cognition. For ARM B, we hypothesise that there will be no change in cognition or measureable cognitive decline. On the basis of our previous work in the Timecourse Trial⁵ and NHMRC-funded SMART Trial³⁸, our proposal is powered for Phase 1 (baseline-FU1) of the trial.

The endpoint of FU2 is designed to assess the magnitude of effect between immediate intervention versus delayed intervention (see Figure 3 and 4). That is, whether the effect size of CCT for ARM B is equivalent to the effect size of CCT for ARM A. We hypothesise that the effect size for those allocated in ARM A will

be greater than ARM B. This is because, as time progresses, the abnormality rates for cognition and other dementia and AD biomarkers increases, thereby making it more difficult to treat. (Figure 1,2)³⁹

Figure 1

[figure not shown]
[figure not shown]
[figure not shown]

Figure 2

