Randomisation will be by computer-generated sequence using small block sizes (n=2), administered by [name]. Allocation will be revealed to the Study Coordinator after the completion of each baseline assessments. A small block size will ensure that the immediate intervention will start relatively immediately.

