6.4 Enrolment and Randomisation Procedures

Following informed consent, the participant's baseline cognitive data from the referring clinic will be collated and checked for completion. Any additional baseline assessments that are not obtained from the referral clinic will be completed and after all baseline data has been collected the statistician will then inform randomisation status (Arm A or Arm B) to the study co-ordinator (by email) who will then book the participant for the appropriate training schedule.

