6.5 Blinding Arrangements

This is a double-blind RCT. Subjects will be informed they will undertake a series of different combination of "brain exercises" of different intensities and will therefore be blind to study hypotheses; expectancies should therefore be well matched. We achieved equivalent insight as to effective treatment status in our NHMRC-funded SMART trial²⁶ between intervention and control groups using this approach. Assessors will be blinded to group status.

NB: As this is a behavioural intervention with no documented risk of adverse events, there are no pre-specified stopping rules or conditions.

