9.6 Un-blinding procedures for adverse events

The code for any participant should only be broken by the chief investigator or authorised person if it is absolutely necessary to ascertain the type of treatment given. The code will be documented and held by the statistician, not to be provided beyond the study co-ordinator (who requires this in order to administer the interventions) until the completion of the trial, or if un-blinding is required. Cases/adverse events that are considered serious, unexpected and probably or definitely related to the treatment will be unblinded by [name] (an independent statistician and holder of the randomisation code). Blinding of all assessors who are in direct contact with the participants will be maintained.

Contact for unblinding:

[name]

Senior Statistical Consultant

Stats Central

Mark Wainwright Analytical Centre

UNSW Sydney NSW 2052

[contact]

m: [name]

www.statscentral.unsw.edu.au

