11. DATA MANAGEMENT

11.1 Data Collection

The Healthy Brain Ageing Clinic: will provide baseline cognitive data in raw and normed scores format for each test and this will be emailed to Trial Co-ordinator.

Similarly, the POWH Memory Clinical will provide baseline cognitive data in raw and normed scores format for each test and this will be emailed to Trial Co-ordinator.

Additional cognitive tests: Amsterdam IADL and Risk Perception test will be administered by the Chief Investigator's team and collated by the Trial Co-ordinator. Composite z-scores for each cognitive domain and global cognition will also be computed by the trial co-ordinator.

DNA APOE information: the saliva DNA extraction kit results will be sent by [name] to Trial Co-ordinator by email.

Sleep-related information (diary, actigraphy and PSQI) will be collected by [name]'s team and email to the Trial Co-ordinator.

All relevant information will be collated by the trial Co-ordinator onto a single password-protected file.

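### Fixed, printed blocks of two make half of all allocations certain in advance to the unmasked coordinator, and the double-blind label does not fit Phase I

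*Protocol*

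**What the plan says.** **Allocation.** Section 4.2 of the Protocol sets the ratio: "Subjects will be randomly allocated in a 1:1 ratio to either ARM A: immediate intervention or ARM B: delayed intervention". Under its Randomisation heading it adds: "Randomisation will be by computer-generated sequence using small block sizes (n=2"). The reason given is: "A small block size will ensure that the immediate intervention will start relatively immediately".

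**Who knows it.** Section 4.2: "Allocation will be revealed to the Study Coordinator after the completion of each baseline assessments". Section 6.4 agrees: "the statistician will then inform randomisation status (Arm A or Arm B) to the study co-ordinator (by email"). Section 9.6 leaves the code with the statistician, "not to be provided beyond the study co-ordinator (who requires this in order to administer the interventions) until the completion of the trial".

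**Who handles the data.** Section 6.4 places collation and a completeness check of the clinic's baseline scores after consent and before randomisation. Section 11.1 has both clinics email those scores to the trial co-ordinator, and continues: "Composite z-scores for each cognitive domain and global cognition will also be computed by the trial co-ordinator". Section 1.4 lists a single co-ordinator.

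**Blinding.** The synopsis and Sections 4.1 and 6.5 call the trial double-blind. Section 6.5 says that participants are told of brain exercises differing in intensity and will "therefore be blind to study hypotheses; expectancies should therefore be well matched"; it also says that assessors are masked. Section 5.1 gives both arms one training prescription and separates them by timing alone. Section 5.1.1 gives the waiting period usual clinic care.

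**The concern.** Concealment means that nobody who can affect enrolment knows the next assignment. With pairs of fixed size, anyone who has seen the first assignment and read Section 4.2 knows the second. The coordinator has seen it by design and also receives candidates' baseline cognitive scores. Recruitment is rolling and clinic tests may be up to 6 months old (Section 6.1), so there is some slack in when a baseline counts as complete. If the coordinator can affect whose baseline closes next, or takes part in consent, the open place could be filled selectively.

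Two further matters touch on masking. The person named to build the primary composite appears to be the one who holds the allocations. And the label claims more than the design delivers. In Phase I one arm attends supervised sessions and the other waits, so mood (GDS), quality of life (WHOQOL), the sleep diary and the PSQI are reported by people who know their arm. A reader of a double-blind trial would not expect that.

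**Working it through.** **Inputs.** Block size 2 and ratio 1:1 (Section 4.2); N = 62 (Sections 4.3 and 10.1).

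**The planned N.** Section 10.1 gives f = 0.22 (read as Cohen's f), two groups, m = 2 time-points, correlation ρ = 0.4 and α = 0.05. For the group-by-time interaction:

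- λ = f²·N·m/(1 − ρ) = 0.0484 × 52 × 2 / 0.6 = 8.39, with 1 and 50 degrees of freedom.
- Power is 0.795 at N = 50, 0.803 at 51 and 0.811 at 52. The smallest even N is 52, as stated.
- 52 / 0.85 = 61.2, rounded up to 62, as stated.

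The required N does not depend on the blocking scheme.

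**Certain allocations, blocks of 2.** 62 / 2 = 31 blocks, each with one free and one determined assignment: 31 / 62 = 50%.

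**Expected correct guesses, blocks of 2.** Guess the arm that is behind, and toss a coin when the arms are level: 31 × 0.5 + 31 × 1 = 46.5, and 46.5 / 62 = 75%.

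**Alternatives.** Fixed sizes were enumerated over all permuted blocks. The mixed scheme was simulated (10,000 runs).

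| Scheme | Certain | Certain of 62 | Guessed correctly |
|---|---|---|---|
| Fixed 2 | 1/2 | 31 | 75% |
| Fixed 4, size known | 1/3 | 20.7 | 70.8% |
| Fixed 6, size known | 1/4 | 15.5 | 68.3% |
| Mixed 4 and 6, sizes withheld | about 1% | about 0.6 | about 69% |

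The 1% counts only moments when the running imbalance has reached its maximum of 3. Someone who also reasoned about where blocks end could be certain more often, so it is a lower bound.

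**Timing of the reveal.** The first member of a pair cannot be deduced, so revealing allocation after baseline protects that person. For the second member the coordinator already knows.

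**Scoring.** Section 8 fixes the tests and the domain weights (40/15/15/15/15%), and masked assessors produce the scores. What remains is data handling, plus one open matter: the synopsis and Section 3.1 include attention and omit visuospatial skills, while Section 8 does the reverse. Whoever builds the composite has to settle that.

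**Blinding passages side by side.** Section 6.5 describes arms that differ in intensity; Section 5.1 says that they differ only in timing. Section 6.5 infers matched expectancy from the SMART trial, but the reference list gives that trial's title as double-sham controlled. A sham comparison cannot vouch for expectancy against a waiting list.

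**The case against.** The best defence is that the route to bias is not documented. Only the coordinator has advance knowledge. Diagnosis is by consensus of several clinicians (Section 4.2), participants are referred by clinics, and consent is taken by an unspecified member of the study team (Section 6.3). This stands as a limit: the harm depends on a role overlap that the Protocol leaves open.

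Several stronger readings are tempting and do not hold:

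- *An assessor unmasked for one participant is unmasked for the pair-mate.* That requires the randomisation order, which nothing in the Protocol gives to assessors.
- *The coordinator can shape the primary score through missing or odd tests.* No such discretion is described, and rules of that kind may sit in an analysis plan not at hand.
- *Revealing allocation after baseline is useless.* It protects half of the participants.
- *Larger varying blocks make allocation unpredictable.* Expected correct guesses fall by only about 6 points; the real gain is in certainty.

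The control condition is also not hidden: the Protocol openly says wait-list, and Section 6.5 explains its claim as blindness to hypotheses. That is true, but it does not amount to participant blinding. The primary outcome is performance-based with masked assessors, so the labelling problem falls mainly on the self-report secondary outcomes.

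Finally, the stated wish for a prompt start is a genuine reason for small blocks. It does not require a fixed, printed size of 2.

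**Conclusion.** The point holds within those limits. With blocks of 2 at 1:1, 31 of 62 allocations (50%) are certain in advance to a coordinator who also receives baseline scores. The share stays 50% if the 32 per arm printed in Figure 3 is used (32 of 64). Selective timing or enrolment is possible, not shown. The scoring risk is secondary and confined to data handling.

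The double-blind label is wrong as written for Phase I: participants are at most blind to hypotheses.

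Two readings are assumed. First, n=2 means one block size of two, which the singular in the sentence that follows supports. Second, the study co-ordinator and the trial co-ordinator are one person, inferred from the single co-ordinator in Section 1.4. A reader might infer that the randomisation is compromised or that the primary result will be biased; nothing in the Protocol shows either.

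**What to change.** 1. For participants not yet randomised, have the statistician generate randomly varying blocks (for example 4 and 6). Withhold the sizes from the coordinator and remove them from the Protocol.
2. Compute the domain and global composites with a locked script on arm-masked data, after reconciling the domain lists in the synopsis, Section 3.1 and Section 8.
3. Relabel the trial as *assessor-blinded, wait-list controlled* in the synopsis and Sections 4.1 and 6.5. Delete the statements in Section 6.5 about differing intensity and matched expectancy. Mark the self-report outcomes as unblinded.

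Cost: a new list and some wording; items 2 and 3 remain possible after recruitment ends. Running imbalance can reach 3 instead of 1, and same-arm runs 6 instead of 2. That slightly weakens the prompt-start reason in Section 4.2 and affects the planning of training slots. The sample size does not change.
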